3.2 Randomization and blinding

The researcher will randomize the patient by using a password-protected randomization service which is part of the clinical data management system "Research Manager". Participants are randomized to either the intervention or the control group, using block randomization, stratified for underlying disease and MUST score (MUST1 or MUST $>$ 1). After randomization, the system provides a trial participants number, who will be documented in a designated source document with the patient information. The study number and birth date will be listed on all study documents. Blinding seems not possible for the coordinating researcher, since one group will receive FoodforCare and the other group will receive no additional products. Whether blinding is possible for the researcher will be examined during the pilot study. In that case, patients will be asked not to tell the researcher in which group they are allocated. Patients have to be aware of the group allocation. Any important protocol modifications will be communicated with the Medical Ethics Committee.

Figure 1. Study design

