4.2 Inclusion criteria

- 18 years or older
- MUST score \geq 1
- living within a 40 km radius around Nijmegen/Veghel
- inclusion at least 4 weeks before surgery
- oral intake
- surgery: Urology, Orthopedics, colorectal and oesophagus.

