6.2 Secondary outcomes

- Functional status: besides HGS, change in functional status will be evaluated with the Short Physical Performance Battery.
- Nutritional status: change in nutritional status will be assessed with the PG-SGA and measurements of body weight (table 1).(18) PG-SGA will be filled in by the patient and a member of the research team. Body weight will be measured on a calibrated weighting scale (type ..) in sober state. Relative weight changes will be presented as the percent weight change relative to the weight at baseline. Body Mass Index will be calculated.
- Nutritional intake: difference in nutritional intake (protein and energy) will be evaluated at every time point based on a 2-day food diary filled in by the patient. The food diary will be cross checked by a member of the research team and, if necessary, the patient will be called for clarification. The food items will be coded and calculated according to the Dutch Food Composition Table (NEVO, RIVM). During the pilot study, we will evaluate if a "symptom diary" should be assessed.
- Length of hospital stay and readmission: reported from the medical record of the patients.
- Postoperative complications: reported from the medical record of the patients and classified using the Clavien-Dindo classification.(19) Grade of severity is based on the type of treatment for the specific complication. Infectious complications will be reported based on the definition of the American College of Chest Physicians/Society of Critical Care Medicine Consensus Conference.(20)
- Quality of life: change of quality of life will we assessed with the SF-36 questionnaire filled in by the patients. The Caregiver Reaction Assessment will be filled in by their caregiver.(21)
- Patient satisfaction:
 - o Both groups will fill in a questionnaire with questions about their wellbeing and stress level regarding shopping and cooking of their meals.
 - o In the intervention group, the Net Promoter Score (NPS) with additional questions will be used to assess patient satisfaction in the intervention group at time point 3. The NPS is determined by asking the question: 'How likely is it

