6.3 Other outcomes

- **MUST:** the Malnutrition Universal Screening Tool will be used at baseline and end of treatment (T2) to determine the risk of malnutrition.
- **Adverse events:** Possible adverse events including nausea, vomiting and gastrointestinal complaints will be identified by the "symptom diary". Unless we do not expect serious adverse events to occur, patients will be asked to contact a staff member and the researcher directly when adverse events occur. We will only report (serious) adverse events that have a possible causal relationship with the given food products till the end of the study. All AEs will be followed until they have abated, or until a stable situation has been reached.

Table 1. Measurements at each time point

	T0		T1	T2	T3
	Preoperative out-patient clinic	Contact by telephone	Baseline	End of treatment	30 days after surgery
Patient information	X				
Informed consent		X			
Randomization		X			
Handgrip strength			X	X	
Weight			X	X	
PG-SGA			X	X	
Nutritional intake			X	X	
Satisfaction				X	
SF-36			X	X	X
SPPB			X	X	X
Postoperative complication					X
Adverse events			X	X	X

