8. STATISTICAL ANALYSIS

8.1 Descriptive statistics

Nominal and ordinal variables will be described using frequency tables, modus and medians. Continuous variables will be described in terms of means and confidence intervals or with medians and range, dependent on normality of the data.

Data will be analyzed using IBM SPSS version 22 for descriptive and statistical analyses. All analyses will be performed according to the intention-to-treat principle.

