8.3 Secondary study parameter(s)

The change in the other parameters for nutritional status between baseline and the end of het intervention will be compared between the control group and the intervention group. The continue variables such as, the change in BMI, quality of life, functional status and patient satisfaction will be analysed by a t-test. The ordinal variable such as, the MUST score and the PG-SGA will be analysed with a Mann-Whitney-U test. The difference in number of patients with a complication will be analysed by a Chi-square test.

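### Section 8.3 compares complications by an unstratified chi-square and leaves out the two factors that stratify randomisation; if those factors predict complications, the test is conservative and loses some power

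*Combined protocol and SAP*

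**What the plan says.** - **Test.** Section 8.3: "The difference in number of patients with a complication will be analysed by a Chi-square test". It names no stratification, no covariate and no time window.
- **Window.** Table 1 (Section 6.3) places the complication assessment at T3, "30 days after surgery".
- **Randomisation.** Section 3.2 assigns patients "using block randomization, stratified for underlying disease and MUST score", with MUST split at 1 versus above 1. The categories of underlying disease are not listed. Section 8 does not mention either factor again.
- **Population.** Section 4.2 admits four surgical fields: "surgery: Urology, Orthopedics, colorectal and oesophagus". Type of surgery is not a named randomisation factor.
- **Grading.** Under Section 6.2, complications are "reported from the medical record of the patients and classified using the Clavien-Dindo classification". No rule reduces several complications in one patient to one value.
- **Ordinal data.** Section 8.1: "Nominal and ordinal variables will be described using frequency tables, modus and medians". Section 8.3: "The ordinal variable such as, the MUST score and the PG-SGA will be analysed with a Mann-Whitney-U test". Clavien-Dindo grade is not among the examples.

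**The concern.** Stratified randomisation balances the arms on the stratifying factors. When those factors also predict the outcome, the difference between arms varies less from trial to trial than it would under simple randomisation. A pooled chi-square does not know this. It takes its variance from the overall complication rate, which still contains the spread between strata. The standard error is then too large, the p-value is too large on average, and a real difference is detected less often than it could be. The information needed to avoid this is recorded for every patient at randomisation.

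A smaller matter sits beside it. Severity grade is collected, but no comparison of grade is specified. If one is wanted, the summary per patient and the method would have to be chosen after the data are available.

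**Working it through.** **What the plan gives.** It states no complication rate, effect size or power for complications. The only sample size is for handgrip strength (Section 4.4): 209 × 1.2 = 250.8, stated as 251; 251 × (1 − 0.3²) = 228.4, stated as 228. That arithmetic reproduces, but it does not size the complication test. With the plan's 20% drop-out, 228 × 0.8 = 182 patients would remain.

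**Assumptions.** Four equal strata with 28 patients per arm in each, so 4 × 2 × 28 = 224, the nearest even split below 228. Control risks are varied over a range. The treatment effect, where present, is a common odds ratio of 0.5. Two-sided 5% level.

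**Type I error by formula.** With balance within strata and no treatment effect, the pooled test uses a variance proportional to p̄(1 − p̄), where p̄ is the mean risk. The true variance is proportional to the mean of p(1 − p) over strata. Let r be the second divided by the first. The actual type I error is then about 2[1 − Φ(1.96/√r)].

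- Equal risks of 35%: r = 0.2275/0.2275 = 1, giving 5.0%.
- 20/30/40/60%: p̄ = 0.375, p̄(1 − p̄) = 0.2344; mean p(1 − p) = (0.16 + 0.21 + 0.24 + 0.24)/4 = 0.2125; r = 0.907; 1.96/√r = 2.058, giving 4.0%.
- 10/15/35/65%: p̄ = 0.3125, p̄(1 − p̄) = 0.2148; mean p(1 − p) = (0.09 + 0.1275 + 0.2275 + 0.2275)/4 = 0.1681; r = 0.783; 1.96/√r = 2.216, giving 2.7%.

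**Simulation**, pooled chi-square against Cochran-Mantel-Haenszel (CMH):

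| Assumed control risks | Type I error, pooled | Type I error, CMH | Power at OR 0.5, pooled | Power at OR 0.5, CMH | Power lost (points) |
|---|---|---|---|---|---|
| 35% in all | 5.3% | about 5% | 64% | 64% | 0 |
| 20/30/40/60% | 3.8% | about 5% | 59% | 62% | 3 |
| 10/15/35/65% | 2.7% | about 5% | 44% | 52% | 9 |

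The last row is 43.5% against 52.4% before rounding. The formula and the simulation agree; the 5.3% with equal risks reflects simulation error and the discreteness of counts. As a deliberately extreme case, risks of 5/10/40/80% give a pooled type I error of 1.2% and power of 25% against 45%, a loss of 20 points. With 184 patients (23 per arm per stratum) and risks of 10/15/35/65%, power is 36% pooled against 44% stratified.

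**What grade would add.** These figures use 228 patients, unstratified tests and an assumed 35% control rate. If all grades shift by a common odds ratio of 0.5, power is 64% for any versus none and 66% for a rank test on grade, a gain of about 2 points. If only severity shifts and the any-complication rate stays the same, the rejection rates are 5% and 11%. Across the severity shifts tried, rank tests on grade rejected about 6 to 14% of the time.

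**The case against.** The strongest reply is that nothing planned here is invalid. The pooled test errs on the safe side, the number of patients with a complication is easy to read clinically, and the plan claims no power for it. The loss depends wholly on how far risks differ between strata. The documents do not give those risks, and with equal risks the loss is zero. The four strata in the calculation are also illustrative, since the protocol's own strata are disease categories it does not list, crossed with MUST. All of this stands, and it limits the point to efficiency.

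A reader might infer more than the text supports:

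- **That the four surgical fields carry very different risks and are pooled despite being strata.** No complication rate appears for any field. The named strata are underlying disease and MUST. Disease may track surgical field, but the protocol does not say so.
- **That severity is discarded.** This is true of the one named test only. Section 8.1 allows grades to be tabulated, and the examples of ordinal variables in Section 8.3 are illustrative, so a test of grade is not excluded.
- **That this is the trial's main clinical outcome.** Section 2.2 lists complications with length of stay and readmissions in the fourth of six secondary objectives.
- **That the introduction expects fewer severe complications.** It links malnutrition to severe complications as a risk, but the benefit it hopes for is fewer postoperative complications in general. Any versus none measures that directly.
- **That grade should replace any versus none because it would reveal a pure shift in severity.** The documents hypothesise no such shift, and the rank test would usually miss it too.

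**Conclusion.** The point holds as one of efficiency. Section 8.3 ignores the two factors used to stratify randomisation. If they predict complications, the planned chi-square is conservative and loses power: 0, 3 or 9 points at an odds ratio of 0.5 under the three main risk patterns, with a true type I error of 5.3%, 3.8% or 2.7%. These sizes rest on four equal strata, balance within strata, a common odds ratio and assumed risks. The documents can confirm none of the risks.

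The test is not biased and alpha is not inflated, so a significant result from it would not be in doubt on this account. The case for also comparing grade is weaker. It would settle in advance how severity is handled, but it gains little power and does not justify changing the endpoint. The amendment is worthwhile because it costs almost nothing, and the trial does not depend on it.

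**What to change.** In Section 8.3:

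1. Keep the number of patients with a complication as the endpoint, and state the window as 30 days after surgery, matching T3 in Table 1.
2. Replace the plain chi-square with a Cochran-Mantel-Haenszel test over the randomisation strata (underlying disease, and MUST 1 versus above 1), or a logistic model with these factors. List the disease categories used at randomisation, so that the strata are fixed in advance. Report the common odds ratio beside the simple percentages per arm.
3. Optionally, add a supporting analysis of each patient's highest Clavien-Dindo grade in the same window, with no complication as the lowest category, by a stratified rank test (van Elteren) or a proportional-odds model with the same factors.

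The cost is one or two sentences. The strata are recorded at randomisation and the grade is already collected under Section 6.2, so no new data and no more patients are needed. The change should be made before outcome data are seen.

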9. ETHICAL CONSIDERATIONS

9.1 Regulation statement

This study will be directed according to the principles of the World Medical Association Declaration of Helsinki (64th WMA General Assembly, October 2013). Additionally, is it in agreement with the Medical Research Involving Human Subjects Act (WMO) and other guidelines, regulations and Acts.

9.2 Recruitment and consent

Patients will be recruited through the department of Medical Oncology at the Radboud University Medical Centre in Nijmegen. All patients admitted to this department en those who meet the inclusion criteria are asked to participate in the study. This request will be discussed with the patient by the nurse or one of the researchers. Additionally, patients will receive a patient information letter with further information about the study. When everything is clear and the patient is willing to participate in the study, the informed consent will be signed. When a patient is enrolled in the study, a personal number is assigned by one of the researchers. The researcher documents the patients' data and the personal number in a designated protected document.

9.3 Objection by minors or incapacitated subjects

Not applicable.

9.4 Compensation for injury

There is a standard liability insurance available at the Radboud University Medical Centre for the study subjects. This is also written in the patient information letter. For the investigators there is also a liability insurance arranged at the Radboud University Medical Centre. In the proposal letter accompanying this protocol, we asked for release of a liability insurance for study subjects because this study includes usual nutritional care and meal service from FoodforCare which is already implemented in the medical centre. The patients will not be exposed to medical treatments during this study.

9.5 Incentives

Patients will not receive financial compensation for participating in the study. They will not have to pay additional hospital visits for this study and thus, they will have no additional travel costs or other costs. However, the intervention group will receive the meals and food products from FoodforCare for free. Due to the measurements that will be performed 3 months after the intervention period, it will not be possible to continue with the FoodforCare meals after this period. Once the effectiveness of FoodforCare at Home has been demonstrated, it is likely that the meals will become available for regular use.

10. ADMINISTRATIVE ASPECTS, MONITORING AND PUBLICATION

10.1 Handling and storage of data and documents

All study documents will be stored in the investigator site file. The informed consent forms will also be stored in Epic. The researchers will enter all data into the database of Castor by means of the study number with their personal password. Only the researchers who are directly involved in the study have access to this program. The key to the codes will be stored in a secure digital environment, so the privacy and anonymity of the patients is ensured. Both the written data and the entered data in Castor will be stored for up to 15 years after the study.

10.2 Monitoring and Quality Assurance

Looking at the directives of the NFU for on-site monitoring, the monitoring-class of the study is negligible. Minimum monitoring is indicated. The monitoring will be performed by an independent gastroenterologist according to the monitoring plan.

Monitor plan

Monitor Frequency	Once halfway the inclusion
Patient flow	Inclusion rate and drop-out percentage
Trial Master File/ Investigator File	Presence and completeness of research file
Informed Consent	100%
In-/exclusie Criteria	First 3 subjects, thereafter 10%
Source Data Verification	10%

10.3 Amendments

Not applicable with first version of the research protocol.

10.4 Annual progress report

The investigator will submit a summary of the progress of the trial to the accredited METC in case the study takes longer than a year. In this report, information will be provided on the date of inclusion of the first subject, numbers of subjects included and numbers of subjects that have completed the trial, serious adverse events/ serious adverse reactions, other problems, and amendments.

10.5 End of study report

The investigator will notify the accredited METC of the end of the study within a period of 8 weeks. The end of the study is defined as the last patient's last visit. For this study, this will be after the last measurement moment of the last patient.

In case the study is ended prematurely, the investigator will notify the accredited METC within 15 days, including the reasons for the premature termination. Within one year after the end of the study, the investigator/sponsor will submit a final study report with the results of the study, including any publications/abstracts of the study, to the accredited METC.

10.6 Public disclosure and publication policy

After analyzing all data, the goal is to present the results on (inter)national conferences and to publish the results in an international journal, independently on positive or negative results of the study. This will be agreed with the sponsor in a contract.

11. STRUCTURED RISK ANALYSIS

11.1 Potential issues of concern

A risk analysis, in respect to the cooperation contract between Maison van den Boer and the Radboud University Nijmegen Medical Centre, will be described in the Aanbiedingnotitie to the Board of Directors and will also be contracted. For example, the risk of financial loss will be clearly described in this contract. This letter will also disclose that FoodforCare has no influence on publishing (positive or negative) results.

11.2 Synthesis

As described previously, we expect that this meal concept will have no additional risk to the patients. In daily practice, the dishes of FoodforCare are widely offered to all patients in the hospital. Matters such as patient safety and hygiene will be respected. In light of these arguments, it does not seem necessary to us to give a structured risk analysis.

